## **Schema**

Prospective double blind placebo controlled trial of 64 patients age 65 and over with a history of cancer who self-report fatigue. After baseline assessment, eligible subjects will be randomized and provided with proprietary MGE pills or placebo to take twice daily for 12 weeks (4 capsules twice daily). Subjects will receive phone call follow-up for toxicity assessment and adherence review at weeks 2, 4, 8. PROMIS Fatigue will also be collected on week 4 and 8 calls. Follow-up assessment will be completed at 12 weeks and a post-treatment assessment at 16 weeks.

Pilot study of muscadine grape extract to improve fatigue among older adult cancer survivors (FOCUS)  
Wake Forest Baptist Comprehensive Cancer Center  
WFBCCC #98320

**Legend:** MGE= muscadine grape extract; PF= physical function testing (SPPD, PAT-D, 6-minute walk); PA=physical activity QOL=quality of life/symptoms; A=adherence, S=symptom review; \*collected by phone

## 1.0 Introduction and Background

Fatigue is the most prevalent symptom among cancer survivors and is commonly associated with aging. Over 40% of community dwelling adults over age 65 reported prevalent fatigue in a recent national survey. Older cancer survivors are therefore at particularly high risk of experiencing persistent fatigue which increases the risk of developing disability. Fatigue is associated with sedentary behavior, decline in physical activity and physical function, poor quality of life and contributes to the phenotype of frailty. This cascade of symptoms and behaviors has negative long-term effects including increased risk of cardiovascular events, decreased muscle mass, increased health care utilization, and mortality risk. Decreasing fatigue could have a significant impact on maintenance of functional independence and overall health for a large proportion of older adults.

Despite the common nature of the symptom, there are few pharmacologic interventions shown to improve fatigue. Treatments for fatigue after exclusion of modifiable medical causes include physical activity, mind body interventions and psychosocial interventions. Despite evidence to support these strategies, these interventions can be resource intensive and difficult for most adults to maintain, particularly older adults. There are no well-tolerated FDA approved medications for treatment of chronic fatigue symptoms. Identifying well-tolerated, efficacious, and cost effective pharmacologic interventions to reduce fatigue is of high priority for the scientific community and of great interest to older adults.

Nutritional interventions and nutraceuticals represent appealing strategies for treatment of fatigue. Biologic mechanisms associated with fatigue are multi-factorial. Common biologic pathways implicated in fatigue symptomatology for both cancer-related and non-cancer related fatigue include systemic inflammation, impairment of mitochondrial function, and cardiac dysfunction. Interventions targeting these pathways may be of particular relevance to older adults given the association between aging and dysregulation of systemic inflammation, mitochondrial function and cardiac health and is in line with the principles of geroscience.

Muscadine grape extract (MGE) is a rich dietary source of bioactive phenols, including ellagic acid, gallic acid, anthocyanins, and flavan-3-ols, which have been studied with particular interest for their potential anti-inflammatory and anti-cancer properties. Preclinical and clinical data from the investigative team show effects of MGE on inflammation, mitochondrial bioenergetics and the symptom of fatigue. This pilot study proposes translation of these observations to a high need clinical setting to test the effect of MGE supplementation on older adults with self-reported fatigue. This study will provide data on the effects of MGE on fatigue, function and biologic correlates to evaluate mechanisms.

[figure not shown]
### 1.1 Preclinical Studies with Proprietary MGE

#### Data from the Investigative Team [name]/[name] Lab:

The MGE administered in the following preclinical studies and Phase 1 clinical trial is a proprietary compound that was prepared from the skins and seeds of muscadine grapes by Piedmont Research and Development Corporation (PRDC). The skins and seeds have high levels of polyphenols, micronutrients found in plants that provide health benefits. The MGE produced by PRDC has a higher concentration of total polyphenols as compared to other muscadine grape nutritional supplements on the market (Figure 1). Mass spectrometry analysis showed that the MGE from PRDC has a higher content of specific polyphenols as compared to other muscadine grape supplements (Figure 2). It should be noted that the proprietary MGE from PRDC is prepared from an aqueous solution of ground seeds and skins; therefore, resveratrol, which has limited solubility in water, was not detected.

[figure not shown]
## 1.2 Rationale for testing MGE to improve fatigue

Several mechanisms to support a potential MGE effect on fatigue have been suggested by pre-clinical studies. Data are highlighted below.

[figure not shown]

**Figure 1.** Total phenolic content of MGEs determined by Folin-Ciocalteu assay using gallic acid as a standard. n=3 separate lots, \*\*\*\*p<0.0001 compared to PRDC.

[figure not shown]
A significant effect of MGE on exercise tolerance, an established fatigue surrogate, was observed in transgenic (mRen2)27, hypertensive female rats administered MGE (0.2 mg total phenolics/mL; in the drinking

[figure not shown]
**Figure 2.** Concentration of specific phenolic compounds in MGEs were determined by ultra-high pressure liquid chromatography/mass spectrometry. n=3 separate lots.

[figure not shown]
**Figure 3.** MGE enhanced exercise capacity (time to fatigue) in female hypertensive rats. n=5; \*\*\*\*<0.0001

**Figure 4.** MGE enhanced exercise workload in female hypertensive rats. n=5; \*\*\*\*<0.0001

**Figure 5.** MGE treated rats had a decreased concentration of urinary 8-OHdG, indicating reduced oxidative stress. n=5; \*p<0.05

[figure not shown]
**Figure 6.** Ang II increased left ventricular filling pressure (E/e'), a measure of diastolic function, while MGE co-administration prevented these effects. E/e' was measured by echocardiography at week 4. \*\*p<0.01 compared with control, # p<0.05 compared to Ang II alone.

water starting at 14 weeks of age after the onset of high blood pressure. At 40 weeks of age (26 weeks of treatment), exercise tolerance was assessed on a treadmill (10.2 m x min, 5% inclination). Time to fatigue (TTF: min) was increased 2.3-fold in MGE-treated animals compared to controls (Figure 3). Workload (W: g X m) was 2.4-fold higher in MGE-treated animals

compared to untreated rats (Figure 4). At the end of the study, there were no significant differences in systolic blood pressure (166 ± 6 vs 162 ± 3 mm Hg) or body weight (365 ± 10 and 385 ± 8 g) between the control rats and the MGE-treated rats. This improvement in exercise tolerance was sustained following 56 weeks of treatment in 70 week-old rats (data not shown), suggesting that MGE consumption improves exercise capacity in aging adult female hypertensive rats independent of changes in blood pressure or body weight. MGE also

Pilot study of muscadine grape extract to improve fatigue among older adult cancer survivors (FOCUS)  
 Wake Forest Baptist Comprehensive Cancer Center  
WFBCCC #98320

reduced urinary 8-OHdG (**Figure 5**), a marker of oxidation, suggesting that oxidative stress may be involved in the improvement in exercise capacity.

**Figure 7.** Ang II increased pulse wave velocity, a measure of arterial stiffness, while co-administration of MGE prevented these effects. \*\*p<0.01 compared with control, #P<0.05 compared to Ang II alone.

[figure not shown]
**To assess the effect of MGE on cardiac damage**, a potential underlying mechanism for fatigue, male Sprague-Dawley rats were pretreated for 1 week with MGE in their drinking water (0.2 mg/mL total phenolics) followed by a 4-week infusion with Ang II (24  $\mu$ g/kg/h) which increased blood pressure from 114 mmHg  $\pm$  1.9 to 211 mmHg  $\pm$  8.5. MGE administration had no effect on blood pressure or systolic function in normotensive or hypertensive rats but ameliorated the Ang II-induced decrease in diastolic function (**Figure 6**) and increase in interstitial cardiac fibrosis by reducing myocardial collagen III and prevented hypertension-induced aortic stiffness (**Figure 7**). These MGE effects were mediated by attenuating Ang II-induced dysregulation of inflammation (NF- $\kappa$ B, IL-6), oxidative stress (Nox, NADPH oxidase, catalase), proliferation (MAP kinase), and fibrotic signaling pathways (TGF- $\beta$ /Smad, CTGF) (data not shown due to page limitations).

These results suggest that MGE may improve patient fatigue by preventing cardiac and vascular damage.

[figure not shown]
**Agents that preserve mitochondrial integrity and maintain or increase mitochondrial respiratory capacity may prevent cardiac tissue damage due to oxidative stress and thereby reduce fatigue.**

Cardiac cells were treated with the redox cycling agent, 2,3 dimethoxynaphthoquinone (DMNQ; 15  $\mu$ M) which generates both superoxide and hydrogen peroxide intracellularly and thus mimics pathologies of elevated reactive oxygen species. DMNQ increased cardiac cell cytotoxicity as measured by LDH release; this effect was prevented by MGE (30  $\mu$ g

pathways (TGF- $\beta$ /Smad, CTGF) (data not shown due to page limitations). These results suggest that MGE

[figure not shown]

**Figure 9.** Mitochondrial metabolism was measured as the Oxygen Consumption Rate (OCR). MGE prevented the DMNQ-mediated reduction in ATP linked to respiration. \*p < 0.05; n=3.

[figure not shown]

**Figure 10.** MGE increased microbial diversity in mouse fecal samples.

total phenolics/mL). DMNQ increased the potential of the mitochondrial membrane, which was also prevented by MGE, suggesting protection of mitochondrial membrane integrity. Cell respirometry measurements showed that DMNQ reduced the oxygen consumption rate (OCR) by 50% (both basal and maximal respiration, **Figure 8**), while co-treatment with MGE prevented this reduction, suggesting that the protective effect may be mediated by preservation of mitochondrial function. MGE prevented the decrease in ATP-linked respiration (**Figure 9**). The basal extracellular acidification rate (ECAR) was increased 2-fold with MGE pretreatment when compared to DMNQ alone ( $13.6 \pm 2.3$  DMNQ+MGE vs.  $6.8 \pm 0.88$  DMNQ, n=3, p<0.01), suggesting that MGE may also increase glycolysis as a response to stress. These data suggest that treatment with MGE enhances mitochondrial function and cellular bioenergetics during

**Figure 8.** Mitochondrial metabolism was measured as the Oxygen Consumption Rate (OCR) by Seahorse analysis. MGE prevented the DMNQ-mediated reduction in basal and maximal respiration rates. \*p < 0.05; n=3.

**Figure 11.** MGE altered the ratio of the relative abundance of Firmicutes to Bacteroidetes

Pilot study of muscadine grape extract to improve fatigue among older adult cancer survivors (FOCUS)  
Wake Forest Baptist Comprehensive Cancer Center  
WFBCCC #98320

oxidative stress and thus may effectively prevent tissue damage from oxidative stress to reduce fatigue. 4T1 Triple negative breast cancer cells were injected into the mammary fat pad of 6-week-old female Balb/c mice. After 2 weeks, tumors were surgically removed and mice received either drinking water or 0.1 mg phenolics/mL of MGE in the drinking water. Mice were sacrificed after 4 weeks; tissues and fecal samples were collected for analysis. Alpha diversity (**Figure 10**) and the Firmicutes to Bacteroidetes ratio (**Figure 11**) were significantly increased in MGE-treated mice compared to the control, indicating enhanced microbial richness and increased energy harvest by the gut microbiome could improve symptoms of fatigue. Butyrate-producing bacteria, such as *Ruminococcus*, *Butyrivibrio* and *Lachnospiraceae*, were increased with MGE ( $p<0.05$ ) as well as the anti-inflammatory compound butyrate compared to other short-chain fatty acids ( $25.0 \pm 2.7\%$  vs  $75.3 \pm 15.5\%$ ;  $p<0.01$ ). Of note, the MGE supplement is a complex mixture of polyphenols that are further metabolized by the host cells or the gut microbiome to secondary and tertiary metabolites, including short chain fatty acids. **These metabolites may serve as additional energy sources, feeding directly into the TCA cycle and leading to enhanced energy production by the mitochondria, to reduce fatigue.**

### 1.3 Clinical Studies with MGE

The investigative team completed a Phase 1 trial (N=23) (ClinicalTrials.gov NCT02583269, IND 128937) in patients with advanced stage solid tumors who progressed on prior therapies (mean age 72 years) to assess the safety and tolerability of proprietary MGE. Five dose levels of the extract from one to five pills twice daily (320 to 1600 mg total phenolics/day) were tested in a standard 3 + 3 design. No concerning safety events were identified; maximum tolerated dose was not reached.

Median time on therapy was 8 weeks, with 29% of patients treated beyond 16 weeks and a median overall survival of 7.2 months. MGE adherence was high (98%) and the most common side effects were flatulence, diarrhea, and constipation. In this heavily pre-treated population, among patients on study at 12 weeks (n=8), **higher dose level of MGE was correlated with increases in the FACT-G score ( $r=0.70$ ,  $p=0.05$ ) and decrease in fatigue ( $r=-0.70$ ,  $p=0.05$ ) (Figure 12)**. In the blood, the mean total phenolic level increased from baseline of 2.12 mg/mL (n = 18, sd = 304) to 2.33 mg/mL at week 8 (n = 16, sd = 245;  $p = 0.01$ ). An MGE breakdown component urolithin A glucuronide, a marker for the ingestion/metabolism of MGE, was measurable in the urine. At baseline, the mean UAG levels were low with a mean of 0.4  $\mu$ g/mL (n=18, sd=1.5) and increased after 8 weeks of MGE treatment to a mean of 17.4  $\mu$ g/mL (n= 16, sd=44.4;  $p <0.01$ ).

#### Additional clinical studies:

The investigative team is currently conducting a double blind randomized trial comparing MGE and placebo among men with prostate cancer (N=160) receiving anti-androgen therapy to evaluate effect on fatigue. Recruitment is on-going (IND 139288, NCT03496805).

### 1.4 Rationale for MGE dosing:

The initial studies looking for an anticancer effect of MGE in both breast and prostate cancer mouse models examined 4 different dose levels: 0.25, 0.5, 1 and 2 mg of phenolics per mouse per day. A statistically significant effect on tumor growth was seen at all 4 dose levels compared to placebo, and while there was a trend toward better efficacy at higher doses, there was no significant difference between the dose levels. An

[figure not shown]

Figure 12

average mouse weighs 0.025 kg, therefore this corresponds to a dose range of 10, 20, 40, and 80 mg of phenolics/kg/day.

A dose 20 mg of phenolics/kg/day was chosen for additional preclinical studies in mice and rats including those reported in 1.2 providing preliminary data for this application. This dose is roughly equivalent to 8 capsules of MGE daily (each capsule contains 500mg MGE which corresponds to approximately 165mg of total phenolics). The phase 1 dose-escalation study with MGE in advanced cancer patients described above evaluated patients at and above this dose level. *Based on the preclinical data and the phase 1 study, 8 capsules of MGE per day was chosen for the phase 2 prostate study and for this proposed pilot, in which effects on fatigue will be assessed in subjects treated for or surviving cancer.*

## 2.0 Objectives

### 2.1 Primary Objective(s)

2.1.1 To evaluate whether administration of MGE supplementation (4 tablets twice daily, approximately 1320mg total phenolics) decreases PROMIS Fatigue score from baseline to 12 weeks compared to placebo.

*Hypothesis: Participants randomized to daily oral MGE administration will experience greater decline in self-reported fatigue (PROMIS Fatigue) from baseline to 12 weeks (primary outcome) compared to those receiving placebo.*

### 2.2 Secondary Objective(s)

2.2.1 To evaluate whether administration of MGE supplementation (4 tablets twice daily) causes changes in physical function (Pepper Assessment Tool for Disability [PAT-D], Short Physical Performance Battery), physical fitness (6-minute walk), physical activity (Minnesota Leisure Questionnaire), and sedentary behavior (Sedentary Behavior Questionnaire) from baseline to 12 weeks compared to placebo.

*Hypothesis: Participants on the intervention will have improved physical function, fitness and activity while sedentary behavior will be lower at 12 weeks compared to the placebo arm.*

2.2.2 To compare changes in health related quality of life (PROMIS Global Health) at 12 weeks in participants randomized to MGE group vs. placebo.

*Hypothesis: Participants on the intervention will report improved quality of life at 12 weeks compared to the control arm.*

2.2.3 To compare changes in the Fried frailty index at 12 weeks in participants randomized to MGE vs. placebo.

*Hypothesis: Participants on the intervention arm will demonstrate improvement in frailty status compared to the placebo arm.*

## **2.3 Exploratory Objectives**

- 2.3.1 To explore whether MGE administration alters 8-hydroxy-2 deoxyguanosine, peripheral blood mitochondrial function, IL-6, TNF-alpha, C-reactive protein, hepatocyte growth factor from baseline to 12 weeks compared to the placebo arm.
- 2.3.2 To explore whether MGE administration alters the microbiome from baseline to 12 weeks compared to the placebo arm.
- 2.3.3 To explore whether 8-hydroxy-2 deoxyguanosine, peripheral blood mitochondrial function, IL-6, TNF-alpha, C-reactive protein, hepatocyte growth factor and the microbiome may mediate changes in self-reported fatigue and physical function, fitness and activity from baseline to 12 weeks.
- 2.3.4 To explore whether MGE administration causes changes in cognitive speed (Digital Symbol Substitution Test) from baseline to 12 weeks compared to placebo.

## **3.0 Patient Selection**

### **3.1 Inclusion Criteria**

- 3.1.1 Self-reported history of cancer diagnosed > 12 months prior to enrollment excluding non-melanoma skin cancer with no evidence of disease at enrollment.
- 3.1.2 Eligible solid tumor cancer types include Stage 1-3 breast, lung, head and neck, colorectal, anal, prostate, melanoma, bladder/ureteral, esophageal, gastric, pancreatic, kidney, liver/biliary, uterine, cervical, ovarian, sarcoma. (superficial disease and in situ disease only is excluded)
- 3.1.3 Eligible hematologic malignancies include lymphoma any subtype any stage in remission, multiple myeloma in remission, leukemia any subtype in remission.
- 3.1.4 Eligible prior cancer treatment modalities include surgery, radiation, chemotherapy, hormonal therapies, immunotherapy, biologic therapies.
- 3.1.5 All anti-cancer therapy completed > 12 months prior to enrollment
- 3.1.6 Age 65 years and older
- 3.1.7 Presence of self-reported fatigue defined by a response of “somewhat, quite a bit or very much” to the screening question “During the past seven days, did you feel fatigued: Not at all, a little bit, somewhat, quite a bit, very much?”
- 3.1.8 Ability to walk without requiring assistance from another individual (use of cane or walker acceptable)
- 3.1.9 Normal organ and marrow function as defined below:

- leukocytes  $\geq 3,000/\text{mcL}$
- absolute neutrophil count  $\geq 1,500/\text{mcL}$
- platelets  $\geq 100,000/\text{mcL}$
- total bilirubin within normal institutional limits
- AST(SGOT)/ALT(SGPT)  $\leq 2.5 \times$  institutional upper limit of normal
- creatinine clearance  $\geq 30 \text{ mL/min}$

3.1.10 Ability to understand and the willingness to sign an IRB-approved informed consent document (either directly or via a legally authorized representative).

## 3.2 Exclusion Criteria

- 3.2.1 active malignancy or on-going cancer treatment including oral anti-estrogen therapy, immunotherapy, biologic therapy.
- 3.2.2 men receiving androgen deprivation therapy
- 3.2.3 use of Coumadin or Warfarin
- 3.2.4 symptomatic congestive heart failure
- 3.2.5 lung disease requiring oxygen
- 3.2.6 end stage renal disease requiring dialysis
- 3.2.7 inability to swallow capsules
- 3.2.8 chronic nausea or diarrhea defined by a frequency of  $\geq$  once per week
- 3.2.9 hemoglobin  $<10 \text{ g/dL}$
- 3.2.10 diagnosis of dementia
- 3.2.11 uncontrolled intercurrent illness including, but not limited to ongoing or active infection, unstable angina pectoris, cardiac arrhythmia, or psychiatric illness/social situations that would limit compliance with study requirements.
- 3.2.12 known untreated hypothyroidism
- 3.2.13 allergy to muscadine grapes or muscadine grape preparations

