### **5.3. Exploratory outcomes**

- 5.3.1 Peripheral blood will be collected at the baseline and week 12 study visit, and will be processed to obtain serum for the measurement of cytokines including interleukin 6 (IL-6), tumor necrosis factor-alpha (TNF- $\alpha$ ), C reactive protein (CRP) and HGF and polymorphonuclear neutrophils (PMNs) to measure mitochondrial function. Cytokines and 8-OHdG will be measured using human ELISA kits (Abcam) and mitochondrial function will be assessed using a Seahorse XF Cell Mito Stress Test (Agilent).
- 5.3.2 Urine will be collected at baseline and 12 weeks to measure the oxidative stress marker 8-OHdG and urolithin A glucuronidate (UAG), a marker for the ingestion/metabolism of MGE. UAG, which is generated from the ingestion of MGE polyphenolic ellagitannins, will be measured using an LCMS-8050 triple quadrupole mass spectrometer in the Wake Forest School of Medicine Proteomics and Metabolomics Shared Resource.
- 5.3.4 Fecal specimens will be collected at baseline and at ~12 weeks using an at-home fecal sampling kit. Samples will be collected by the patient prior to the initiation of intervention and again near the completion of intervention. Patients will be asked to mail samples in a pre-paid package to the laboratory. DNA will be isolated from fecal samples using the Qiagen DNeasy PowerSoil Pro kit protocol. Metagenomic sequencing will be performed by CosmosID Inc. (Rockville, MD). In brief, DNA libraries will be prepared using the Illumina Nextera XT library preparation kit, with a modified protocol. Library quantity will be assessed with Qubit (ThermoFisher). Libraries will be sequenced on an Illumina HiSeq platform 2x150bp. Fecal samples will be read at 12M read-depth. Unassembled sequencing reads will be directly analyzed by CosmosID bioinformatics platform for multikingdom microbiome analysis and quantification of organism's relative abundance. Fecal microbiomes will be assessed by metagenomic sequencing and bioinformatics. A list of all the microbiologic species will be recorded, along with their relative abundance recorded as a % relative abundance of the total microbiome.
- 5.3.5 Digit Symbol Substitution Test (DSST) is a measure of attention and perceptual speed, amenable to change with exercise or fatigue in which participants are given a

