#### **5.4. Adverse events (AEs)**

AEs will be assessed by the study team at each visit (by phone or in person). AEs of interest are flatulence, diarrhea, nausea, dyspepsia, constipation, abdominal pain (see Appendix P). Other possibly/probably attributable adverse events will be recorded in addition to any serious adverse event.

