## 6.0 Intervention Plan

### 6.1 Study-Related Activities

Measures / Timepoints	Pre-Study a	Baseline	Wk 2	Wk 4	Wk 8	Wk 12	End of Trtmt Visit h
Informed consent	X						
Medical and oncologic history	X						
Concomitant medications assessed by self-report j	X	X	X	X	X	X g, j	
Karnofsky Self-Reported Performance Rating Scale		X					
Vital signs		X					X j
Adverse event assessment		X	X	X	X	X g, j	X
Drug dispensing b		X					
Pill count							X g, j
Telephone follow-up c			X	X	X		
Cognitive/Physical function & fitness (DSST, SPPB, 6-min walk, grip strength)		X					X j
CBC with differential d	X						X j
Serum chemistries d	X						X j
(Partially fasting) labs for phenolic levels (blood and urine) e		X					X j
(Partially fasting) labs for correlative studies e (blood and urine)		X					X j
Stool sample collection f		X					X j
PROMIS Fatigue survey		X	X	X	X	X g, j	X
Other patient reported outcomes (PAT-D, LASA, PROMIS Global Health, CES-D, MLTA, Self-reported weight loss) j		X					X g, j
Participant Feedback							X i, j

a Labs to assess eligibility must be completed within 30 days prior to the first dose of MGE/placebo.

b Study drug (MGE or placebo) will be dispensed as a 90-day supply at the baseline visit.

c Adherence and symptom review will be assessed at each study visit. In addition, participants will be contacted by phone as follows,  $\pm 3$  days: Wk2, Wk4, Wk8.

d Safety laboratory assessments must be done within 30 days of first dose of MGE/placebo and then on the study visits indicated. These labs include:

Complete blood count (CBC) with differential: WBC count with differential, platelet count, hemoglobin/hematocrit.

Serum chemistries (complete metabolic panel, CMP): sodium, potassium, chloride, bicarbonate, blood urea nitrogen, creatinine with creatinine clearance, glucose, aspartate aminotransferase (AST), alanine aminotransferase (ALT), total bilirubin, alkaline phosphatase.

e Phenolic levels and other research labs will be obtained at baseline, and 12 weeks ( $\pm 14$  days). Patients are asked to avoid coffee, tea, fruit juice, fruit, chocolate or wine after midnight prior to blood draw.

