f Two kits will be provided to participant at baseline, with detailed instructions for how and when to collect stool at home.

g If a participant is unable to attend an in person study visit for any reason including COVID-19 related reasons, all patient reported measures will be collected in a phone study visit.

- h End of Treatment Visit will be conducted by phone 30 days (+14 day window) after last dose of study medication. For those who end treatment prior to week 12, the End of Treatment Visit can be combined with another existing study visit, if that visit occurs 30-44 days after the last dose of study medication.
- i Participant feedback will be collected in person at Wk12 visit (+30 day window), or by phone at Wk16.
- j Follow-up study visits will occur at 12 weeks and will have a  $\pm$ 14 day allowance window which includes not just the visit itself, but any of the activities at that visit. For example, if labs cannot be collected at the actual study visit, the  $\pm$ 14-day window permits a second attempt at lab collection; all activities, however, must be completed in the  $\pm$ 14-day window from the expected visit date.

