### **12.3 Analysis of Exploratory Objectives**

To analyze the biomarker outcomes in Objective 2.3.1, which are measured continuously, we will also use the ANCOVA approach described for the secondary objectives, and will construct 95% for the differences in the change between the two groups at 12 weeks.

To meet Objective 2.3.2, we will examine the proportion of different bacteria taxa at each time point, and will use a marginalized two-part beta regression model to account for the compositional nature of the data. If we are unable to fit this model, we will examine changes using McNemar-Bowker tests for within-person changes and for mammary and gut composition at 12 weeks.

To meet Objective 2.3.3, we will include the biomarker data in the models of the primary and secondary outcomes described above, and evaluate if the effects of the intervention on each outcome is attenuated in the presence of the biomarker. Attenuation of 10% or more in the intervention parameter estimate will indicate potential mediation in the presence of a clinically meaningful change of both the primary or secondary outcome and the biomarker of interest.

For Objective 2.3.4, we will compare the change in the DSST score between the 2 groups at 12 weeks, using a mixed model with linear contrasts.

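### Acute infection, vaccination and antibiotic use around the exploratory samples are not asked about for sampling or handled in section 12.3; a flag is a cheap improvement, mainly for the mediation analysis

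*Combined protocol and SAP*

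**What the plan says.** **Entry.** Section 3.2.11 excludes "uncontrolled intercurrent illness including, but not limited to ongoing or active infection". Vaccination and antibiotics are not named there or elsewhere.

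**Sampling.** Section 5.3.1: "Peripheral blood will be collected at the baseline and week 12 study visit". There is thus one post-baseline blood sample. Stool is collected at home: "Samples will be collected by the patient prior to the initiation of intervention and again near the completion of intervention" (5.3.4). The only pre-draw instruction in section 6.1 is dietary: "Patients are asked to avoid coffee, tea, fruit juice, fruit, chocolate or wine after midnight prior to blood draw". Footnote j allows a second attempt within 14 days either side of the expected visit, "if labs cannot be collected at the actual study visit". Footnote g moves patient-reported measures to the phone for anyone unable to attend, COVID-19 included.

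**Recording.** The calendar in 6.1 has a self-report of concomitant medications at pre-study, baseline and weeks 2, 4, 8 and 12, and section 11.0 lists a form for it. Section 5.4 covers a list of gastrointestinal events, and then: "Other possibly/probably attributable adverse events will be recorded in addition to any serious adverse event".

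**Analysis.** Objective 2.3.1 concerns 8-OHdG and "peripheral blood mitochondrial function, IL-6, TNF-alpha, C-reactive protein, hepatocyte growth factor from baseline to 12 weeks compared to the placebo arm". Section 12.3 analyses these by ANCOVA. For mediation (2.3.3), "we will include the biomarker data in the models of the primary and secondary outcomes described above". Attenuation of at least 10% in the treatment estimate then indicates potential mediation, provided that outcome and biomarker both change by a clinically meaningful amount. No flag, covariate or sensitivity analysis for acute events is given.

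**The concern.** CRP, IL-6, TNF-alpha, neutrophil function and the gut microbiome can all respond to a recent infection, vaccination or antibiotic course. With a single follow-up sample, one affected value has no second reading to offset it.

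The consequence differs by objective. In 2.3.1 and 2.3.2 the arms are randomised and blinded, so such events should strike both arms alike and cost precision. Randomisation gives no such protection in 2.3.3. An acute illness that raises both the marker and fatigue creates an association between them with no causal path from one to the other. If MGE also lowers the marker, adjusting for the marker then takes away part of the treatment effect, and the 10% rule can read this as mediation. A question about acute illness that was not asked at the visit cannot reliably be answered later.

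**Working it through.** **1. The plan's own figures (section 12.4) reproduce.** Upper limit of the SD: 6.4 × √(11 / 5.578) = 8.99 (stated 9.0), where 5.578 is the 10th percentile of chi-square with 11 df. Effect size: 3 / 9.0 = 0.33. One-sided 90% bound: 1.2816 × √(2/30) = 0.331 (stated 0.33). Dropout: 30 / 0.95 = 31.6, so 32 per group. Nothing below changes these figures.

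**2. Arm comparison (2.3.1, 2.3.2).** The documents give no rate or size for acute events. I assume a share p of each arm affected and a marker shift of k SD. Expected bias is 0 when p is equal in the arms. The SD is multiplied by √(1 + p(1−p)k²):
- p = 3%, k = 1: 1.01
- p = 10%, k = 2: 1.17
- p = 15%, k = 3: 1.47

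The chance that two arms of 30 differ by three or more affected people is 6%, 13%, 27.5% and 36% for p = 3%, 5%, 10% and 15%.

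**3. Mediation (2.3.3), expected false attenuation.** Assumptions, none from the documents: log-marker SD 1.0; baseline correlation 0.7, so residual variance 1 − 0.49 = 0.51; infection multiplies the marker by 10 (ln 10 = 2.303) and adds 5 fatigue points; the MGE effect on fatigue is 3 points; the marker has no causal effect on fatigue.

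False slope = p(1−p) × 2.303 × 5 / [0.51 + p(1−p) × 2.303²]
- p = 3%: 0.335 / 0.664 = 0.50
- p = 5%: 0.547 / 0.762 = 0.72
- p = 10%: 1.036 / 0.987 = 1.05

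Attenuation = slope × |log effect of MGE on the marker| / 3. Reductions of 20%, 30% and 40% are log effects of 0.223, 0.357 and 0.511.

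| MGE lowers marker by | 3% infected | 5% | 10% |
|---|---|---|---|
| 20% | 3.8% | 5.3% | 7.8% |
| 30% | 6.0% | 8.5% | 12.5% |
| 40% | 8.6% | 12.2% | 17.9% |

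Three of nine cells exceed 10%. The 0.51 presumes that the 2.3.3 models adjust for the baseline marker, which section 12.3 does not say. Without it the denominator starts at 1.0, and only the last cell stays above: 1.036 / 1.477 = 0.70, and 0.70 × 0.511 / 3 = 11.9%.

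**4. Mediation, chance of crossing 10% in one trial.** Simulation with 30 per arm, 20,000 runs, fatigue SD 9, MGE effect −3, no causal marker path, and the 10% condition alone:

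| Acute events | MGE does not move marker | MGE lowers marker 0.33 SD | 0.5 SD |
|---|---|---|---|
| none | 14% | 22% | 28% |
| 5%, 2 SD, fatigue +5 | 15% | 27% | 35% |
| 10%, 2 SD, fatigue +5 | 17% | 32% | 41% |
| 10%, 2 SD, fatigue +10 | 22% | 45% | 57% |
| 15%, 3 SD, fatigue +10 | 32% | 55% | 67% |

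Mean false attenuation is about 0 in the first column. In the 0.33 SD column it is 0%, 4%, 7%, 14% and 19%, reading down.

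**The case against.** Several counter-arguments stand and limit the point.

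- **Recording.** A reader might infer that these events go largely unrecorded. The documents do not support that. Antibiotics should be caught by the medication self-report, serious events are recorded, a follow-up CBC with differential is taken, and symptoms are reviewed at each visit (6.1, footnote c). What lacks an explicit record is vaccination and non-serious infection not attributed to the capsules.
- **Distortion.** A reader might infer that the marker and microbiome comparisons are biased. With 1:1 double-blind allocation and equal event rates, expected bias is zero.
- **Baseline against week 12.** A reader might infer that 3.2.11 protects baseline and leaves only week 12 exposed. It excludes uncontrolled illness, with infection as an example, and it is not a sampling rule. Both samples lack a rule.
- **COVID-19.** It would be wrong to say that ill participants are all sampled as usual. Those unable to attend move to a phone visit under footnote g. Someone mildly ill who attends is still sampled.
- **Forms elsewhere.** The note under the table of contents says that coordinator and nursing forms were moved out of the protocol. Section 10.0 refers to a collection protocol agreed with the study team and to stool-kit instructions. A pre-sampling question may exist there. Even so, section 12.3 makes no use of one.
- **The rule itself.** The 10% criterion gives 14-28% false signals at this size without any acute events, so small numbers are the larger weakness. The condition of clinically meaningful change would lower all these probabilities.

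**Conclusion.** The point holds as a cheap improvement to the exploratory objectives. The documents do not ask about acute infection or vaccination at either sampling visit, do not link the antibiotic data they should hold to the samples, and give section 12.3 no handling for any of the three. The cost for 2.3.1 and 2.3.2 is precision: an SD 1% to 47% larger over the assumed range. For 2.3.3 the issue is potential confounding, with expected false attenuation of about 4-18%, above 10% in 3 of 9 scenarios. That result needs MGE to lower the marker; if it does not, mean false attenuation is about zero. Event rate, marker rise and fatigue rise are all assumptions, and effects on the microbiome, on neutrophil function and of vaccination were not quantified. The primary and secondary analyses and the sample size are unaffected.

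**What to change.** At the baseline and week-12 sampling visits, record two yes/no items: acute infection or vaccination in the last 14 days, and antibiotic use in the last 4 weeks, cross-checked against the medication self-report. Record the date of last dose as well, and flag affected blood and stool samples.

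In section 12.3:
- repeat the 2.3.1 and 2.3.2 analyses without flagged samples, as a sensitivity analysis;
- include the flag as a covariate in the 2.3.3 models;
- draw no mediation conclusion that depends on flagged samples.

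Do not make deferral a rule. A 28-day antibiotic look-back cannot generally clear within a 14-day allowance. Late sampling can also fall after the last dose: week 12 is day 84, the window runs to day 98, and a 90-day supply taken in full ends 8 days before that. Any re-sampling under footnote j should be optional, with its timing relative to the last dose recorded.

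The cost is two form items, one date, a small extra analysis, and slightly fewer samples in the sensitivity analysis.
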